6. GENERAL CONVENTIONS

Unless otherwise stated, all analyses will be performed using SAS Version 9.2, and all hypothesis tests will be conducted at a two-sided significance level of 0.05. P-values will be presented with 3 decimal places, and p-values that are less than 0.001 will be presented as <0.001.

Continuous (non-survival-related) data will be summarized using descriptive statistics: number of observations (n), mean, standard deviation (SD), median, minimum and maximum. Frequencies and percentages will be used to summarize categorical (discrete) data. Presentations of categorical data will generally suppress percentages for items where the count is zero, in order to draw attention to the nonzero counts. In general, mean, SD, median, minimum, maximum and percentages will be presented with one decimal place.

Unless otherwise stated, confidence intervals, when presented, will be constructed at the two-sided 95% level. For binomial variables, the 95% confidence intervals will be constructed using the normal approximation without continuity correction.

Data listings will present all data collected on Case Report Forms (CRFs) by study drug, center and subject number. Unless otherwise stated, data will be presented by treatment and overall.

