9.2 DERIVATION OF THE PRIMARY EFFICACY VARIABLE

WAAPI scores will be calculated for each weekly interval (i.e., 7-day intervals) relative to randomization date (first randomized treatment date) for all subjects (both subjects on q1w and q4w). For example, WAAPI at Week 0 will be the average of available (non-missing) APIs captured during the 7 days prior to Treatment Day 1 (the first randomized treatment day). WAAPI at Week 1 will be the average for the next 7 days including the score captured on Day 1. WAAPI at Week 12 (the primary timepoint) will be the average for the APIs captured from Day 78 to Day 84. The baseline WAAPI score will be the WAAPI at Week 0. The changes from baseline at any post-baseline timepoint will be calculated as baseline minus post-baseline, so that a positive change is indicative of improvement.

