9.3 PRIMARY ANALYSIS

The primary analysis will be performed based on the mITT Population.

WAAPI over time will be performed by longitudinal data analysis using mixed-model repeated measures (MMRM) methods. All post-randomization baseline observations will be utilized; missing values will remain as missing (i.e. no attempt will be made to impute missing values, and only observed values will be used in the data analysis). The model will include treatment, post-baseline weeks, treatment by week interaction as fixed effects, and baseline WAAPI as the covariate. The covariance will assume to be unstructured. If the estimates do not converge, SAS default covariance structure (variance components) will be assumed. The MMRM with maximum likelihood estimation will utilize the following pseudo-SAS code for analysis:

```
proc mixed data = WAAPI Data method = ml;
class treatment week subject;
model Change in WAAPI = treatment week treatment*week baseline;
repeated week / subject = subject type = un;
lsmeans treatment / pdiff cl e;
lsmeans treatment*week /slice = week cl diff;
ods output diffs = alldiff;
```

If the estimation under type=un cannot converge, the SAS default (variance components) will be used. The estimated treatment effects, treatment differences, and the two-sided 95% confidence intervals of the treatment differences at all post-baseline timepoints will be presented. The primary comparison will be the treatment difference at Week 12.

A clear advantage of using MMRM is that this method does not require artificial missing imputations that would often create biases. The MMRM method is valid if the “missing at random” assumption holds. The trial is designed to minimize missing values: (a) Subjects who discontinue taking study medication are permitted to remain in the study, and safety and efficacy data will continue to be collected from these subjects; (b) Liberal use of rescue medication is allowed during the study, and data collection will continue even after subjects take these medications, and (c) Robust efficacy data collection procedures will be used in the trial.

Using the procedures above, it is expected that missing values will be minimal and that “missing at random” is a reasonable assumption. Therefore, the “MMRM without missing” imputation is reasonable. Sensitivity analyses of missing value imputations will be performed to support the robustness of the conclusion (see [Section 9.4](#)).

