9.9 POWER AND SAMPLE SIZE JUSTIFICATION

A sample size of 170 subjects per treatment group will provide over 90% power to detect a treatment difference at a two-sided 5% significance level. In the sample size calculation, a treatment difference of 0.7 units and an SD of 2 (or a standardized effect of 0.35) for the primary efficacy variable were assumed.

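### The primary MMRM fixes one baseline slope for Weeks 1 to 12; adding baseline-by-week recovers some precision and guards against a Week 12 bias that can go either way

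*SAP*

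**What the plan says.** SAP 9.3 analyses change in WAAPI with fixed effects for treatment, week and their interaction, plus baseline WAAPI as one covariate: "model Change in WAAPI = treatment week treatment*week baseline". Estimation is by maximum likelihood, "proc mixed data = WAAPI Data method = ml", with an unstructured covariance, "repeated week / subject = subject type = un". Neither the text nor the code names a degrees-of-freedom method, so the software default applies. Of the 12 weekly differences, one is confirmatory: "The primary comparison will be the treatment difference at Week 12". SAP 9.2 defines change as baseline minus follow-up, "so that a positive change is indicative of improvement", so an estimate above the true difference favours active. SAP 9.8 places this test first in a fixed sequence. SAP 9.3 expects few missing values and rests the model on data being missing at random. Neither document gives a dropout rate, a baseline SD or a correlation between baseline and later weeks.

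**The concern.** Because the outcome is baseline minus follow-up, its slope on baseline equals one minus the slope of the pain level on baseline. Week 1 adjoins the baseline week, whereas Week 12 covers Days 78 to 84. If pain follows baseline less closely as time passes, the slope of change on baseline rises from week to week. The model lets everything else differ by week, but not this.

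Write b for the common slope and s12 for the true Week 12 slope. The Week 12 mean is then misfitted by (s12 - b) x (baseline - mean baseline). With complete data, randomisation balances baseline and the misfit only adds noise. If dropout depends on baseline or on earlier pain, and does so differently by arm, the subjects still observed at Week 12 differ in baseline between arms and the misfit enters the treatment difference. For example, if high-baseline subjects leave placebo, those remaining have lower baselines, the placebo mean change is understated and the difference is overstated. If they leave active, the error reverses.

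At stake is the test on which every later claim in SAP 9.8 depends. No sensitivity analysis in SAP 9.4 changes the baseline term. The two imputation methods there alter the missing-data assumption at the same time, so they would not isolate this problem.

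**Working it through.** **The plan's own figure.** SAP 9.9: "A sample size of 170 subjects per treatment group will provide over 90% power", for a difference of 0.7 and an SD of 2, with tests two-sided at 0.05 (SAP 6).
- SE = 2 x sqrt(2/170) = 0.2169, and 0.7/0.2169 = 3.227.
- Power = Phi(3.227 - 1.960) = Phi(1.267) = 0.897. Exact 90% needs 172 per arm. The figure is reproduced within rounding.

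**Inputs from the documents.** The model, the Week 12 contrast and the sign convention (SAP 9.2, 9.3); 1:1 allocation (SAP 4.4); a 7-day pain score of 4 or less at randomisation (Protocol 7.4). The analysed number is below 340 by an unstated amount, because SAP 5.2 excludes two sites.

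**Assumed inputs.** Week 12 SD 2.0; baseline SD 0.8 to 1.2; slope of change on baseline 0.1 at Week 1, rising to 0.3, 0.6 or 0.9 at Week 12; dropout either 0% or 21 to 46% by arm.

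**Large-sample bias of the common-slope model** (1,000,000 simulated subjects per scenario). The fitted common slope was 0.02 to 0.13, close to the Week 1 value and well below the Week 12 value.

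| Assumed exit mechanism | Bias in Week 12 difference |
|---|---|
| None, or completely random (even if rates differ by arm) | about 0 |
| Same rule on last pain score in both arms | +0.004 to +0.03 |
| High pain, more so in placebo | +0.02 to +0.16 |
| High baseline, in placebo | +0.04 to +0.20 |
| High pain in placebo, low pain in active | +0.03 to +0.22 |
| Change from baseline | -0.012 to +0.001 |
| High baseline, in active | -0.025 to -0.14 |

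With baseline*week and REML, the bias was within 0.01 in every missing-at-random scenario.

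**Trials of 340 subjects** (baseline SD 1.0, slope 0.1 rising to 0.6; 3,000 trials under no effect, 1,500 at 0.7). Each cell gives the SAP model, then the model with baseline*week and REML.

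| Case | Bias | Mean SE | Rejection |
|---|---|---|---|
| No dropout, no effect | +0.007 / +0.007 | 0.2187 / 0.2126 | 5.5% / 5.1% |
| Completely random, no effect | 0.000 / +0.001 | 0.2443 / 0.2381 | 5.3% / 4.9% |
| Same pain rule in both arms, no effect | +0.001 / +0.002 | 0.2491 / 0.2411 | 5.0% / 5.3% |
| Placebo exits more pain-driven, no effect | +0.072 / +0.001 | 0.2518 / 0.2445 | 6.1% / 5.1% |
| High-baseline exits from active, no effect | -0.078 / +0.004 | 0.2441 / 0.2394 | 6.0% / 5.0% |
| Placebo exits more pain-driven, true 0.7 | +0.073 / 0.000 | 0.2504 / 0.2431 | 87.1% / 81.3% |

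Monte Carlo error is about 0.004 to 0.006 for bias and 0.4 points for null rejection.

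- Precision: 0.2187/0.2126 = 1.029 with no dropout, and 1.020 to 1.033 across the null rows. Over all scenarios the ratio was 0.995 to 1.06 in most and 1.13 at the extreme of slope drift and baseline SD.
- Check on the 6.1%: the shift is 0.0716/0.2518 = 0.284 SE. Then Phi(-1.960 + 0.284) + Phi(-1.960 - 0.284) = 0.047 + 0.012 = 5.9%. False rejections in favour of active are thus about 4.7% instead of 2.5%.
- In the last row, the higher rejection rate of the SAP model comes mainly from the bias; it is not a gain in power.

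**Maximum likelihood and degrees of freedom.**
- The simulated ratio of ML to REML standard errors was 0.996 to 0.997; sqrt(337/340) = 0.9956. The change in null rejection was 0.0 to 0.15 points.
- The SAP model's SE was 0.994 to 1.005 of the empirical SD.
- The critical t is 1.967 at 337 df and 1.972 at 200 df.
- Kenward-Roger was not fitted in these runs. A separate simulation put the ML standard error below it by 1 - 0.2355/0.2375 = 0.8% at 30% dropout, and by 1.7% at 49% dropout with 150 per arm. Those figures were not independently repeated.

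**The case against.** The strongest reply is that every magnitude above rests on inputs the documents do not contain. Nothing in them shows that the baseline slope drifts. SAP 9.3 expects few missing values and allows subjects who stop study drug to stay in follow-up. If dropout is small or unrelated to pain, the bias disappears and only a modest loss of precision remains. This stands, and it is why the point is conditional.

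Two stronger readings are tempting, and the documents support neither.

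- A reader might infer that the model is biased toward active by construction. It is not: the bias is about zero without informative dropout, and its sign follows the mechanism. Protocol 8.1.5 anticipates rising pain on placebo, Protocol 8.1.4 has subjects whose rescue need passes the limit asked whether to continue, and Protocol 7.7 lists lack of efficacy as a reason to discontinue. These make pain-driven placebo exits plausible. They do not establish them, or exclude the reverse.
- A reader might infer that maximum likelihood with default degrees of freedom makes the standard errors materially too small. The direction is right, but 0.3 to 0.4% against REML is negligible at this sample size. It also partly offsets the wider contrast in the reported interval: in the separate simulation the SAP's SE of 0.2355 compares with 0.2332 for the full correction, about 1%.

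It would also go too far to extend the figures to all endpoints analysed by similar methods. EQ-5D-5L, WPAI and PGI-I are collected every four weeks in the double-blind phase (Protocol Tables 6 and 7), and none was simulated.

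**Conclusion.** The point holds as a conditional weakness that costs almost nothing to remove. If the slope of change on baseline drifts, the common slope loses some Week 12 precision. If dropout also depends on pain or baseline differently by arm, it can shift the primary estimate in either direction. In the central case the shift is about 0.07 to 0.08, roughly a tenth of the design effect (0.07/0.7 = 0.10), with null rejection near 6%. The baseline-by-week model restored rejection to 4.9 to 5.3%. The size and sign in this trial cannot be derived from the documents. The estimation method and degrees of freedom are a matter of good practice only.

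**What to change.** Before unblinding, revise SAP 9.3 to add `baseline*week` to the model statement and say so in the text. In the same edit, change the estimation option to `method=reml` and add `ddfm=kr`. Use the same model for the weekly worst-pain endpoint in SAP 9.5.1; the effect on the other secondary endpoints was not assessed. Protocol 11.1 leaves the analysis detail to the SAP, and SAP 6.2 provides for numbered revisions after the final version.

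The cost is 11 more mean parameters (12 slopes in place of one) among about 340 subjects, and no new data. The sponsor should know that if placebo exits are pain-driven, the corrected model can lower the chance of a significant result (87.1% to 81.3% in the simulated case), because it removes an upward bias.

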7.7. Removal of Subjects from Therapy or Assessment

A subject is free to withdraw his/her consent and discontinue participation in the study at any time for any reason. A subject's participation must therefore be terminated immediately upon his/her request, and the reason(s) for discontinuation appropriately documented.

A subject must be discontinued from the study, including the Titration, Double-Blind Phases, and Open-Label Safety Extension Phase, for any of the following reasons:

- Safety reasons, including AEs or significant concomitant illness, injury or urgent surgeries/procedures that would, in the judgment of the investigator, affect assessments of clinical status to a significant extent, require discontinuation of study drug, or both
 - Every attempt should be made to collect samples for a urine toxicology test and BPN blood concentration if a subject experiences a SAE or is discontinued from the study due to an AE. The investigator will remain blinded to the results until the study blind is broken.

- At the request of the Sponsor, regulatory agency, or Institutional Review Board (IRB)
- Subject is lost to follow-up
- Subject treatment allocation is unblinded
- Death of subject

A subject may also be discontinued from the study, at the discretion of the investigator and/or Sponsor, for any of the following reasons:

- Lack of efficacy
- Subject refuses or is unable to adhere to the study protocol visits and procedure
- Major protocol violation
- Pregnancy
- Use of unacceptable concomitant medication(s)
- It is not considered in the best interest of the subject to continue
- Administrative reasons (e.g., termination of enrollment or study)

The investigator must maintain a record of all subjects who discontinue from the study prior to completion. The reason(s) for study discontinuation will be documented. In the event that a subject chooses to withdraw from the study, the Investigator should make a reasonable attempt to obtain and record the reason(s) for withdrawal in as much detail as possible, although the subject is not obligated to provide such reason(s).

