In addition, at any time during the Double-Blind Phase, if the subject requires rescue medication above the maximum allowable (hydrocodone/acetaminophen 30 mg/1950 mg/day (six tablets) for subjects whose screening MED was ≥ 80 mg/day; or 15mg/975 mg/day (three tablets) for subjects whose screening MED was between 40 and 79 mg/day), the subject should be asked if they want to continue with the maximum dose of rescue medication or would like to withdraw from the study. If circumstances surrounding discontinuation or withdrawal are unclear, the Medical Monitor should be consulted. If the subject decides to withdraw, the subject should have a final on-treatment visit and then have procedures and assessments completed for any remaining study visits, as specified in the protocol.

Telephone or other contacts made by the site are allowed throughout the course of the study. Subjects should return to the study center according to the schedule specified in this protocol.

One week after the last dose of CAM2038/placebo q1w or 4 weeks after the last dose of CAM2038/placebo q4w, the subjects will attend a Final Study Visit. At the Final Study Visit (or early termination), subjects will be transitioned back to standard care or their treatment prior to study entry. Within 4 weeks after the Final Study Visit, subjects will be contacted by phone to assess AEs and review concomitant medications.

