8.1.5. Subjects Randomized to Placebo in the Double-Blind Phase

At the start of the Double-Blind Phase, approximately half of the subjects (170) will be randomized to placebo. These subjects may experience increases in their pain scores and require rescue medication. Sites are encouraged to keep these subjects in the study as long as possible. However, subjects may withdraw consent for participation at any time and for any reason. Subjects who discontinue prematurely may be replaced at the discretion of the Medical Monitor and the Principal investigator, in order to maintain study power.

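### The q1w/q4w randomisation stratum is missing from the primary model and the main secondary tests (no bias, a small loss of power); separately, the unlikely fallback to variance components would remove the missing-at-random protection at Week 12

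*SAP*

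**What the plan says.** **Stratum.** Protocol 8.3 stratifies randomisation by double-blind dosing regimen, and SAP 4.4 randomises 1:1 within q1w and within q4w. SAP 9.3 then specifies: "The model will include treatment, post-baseline weeks, treatment by week interaction as fixed effects, and baseline WAAPI as the covariate". Regimen is in neither the model statement nor the CLASS statement. The responder analyses (SAP 9.5.2 and 9.6.1) use a plain chi-square test, and time to loss of efficacy (SAP 9.5.3) uses a log-rank test with treatment only. SAP 9.4 contains no regimen-adjusted analysis.

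**Fallback.** The first choice is REPEATED with TYPE=UN, fitted by maximum likelihood, with missing values not imputed because the method is valid under missing at random. The replacement rule is stated twice: "If the estimates do not converge, SAS default covariance structure (variance components) will be assumed", and after the code, "If the estimation under type=un cannot converge, the SAS default (variance components) will be used". There is no intermediate structure, no RANDOM statement and no robust standard error.

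**Missing data.** The plan takes steps to limit loss. SAP 9.3 says: "Subjects who discontinue taking study medication are permitted to remain in the study". Protocol 8.1.5 says of placebo subjects: "These subjects may experience increases in their pain scores and require rescue medication", and adds: "Sites are encouraged to keep these subjects in the study as long as possible". Under Protocol 8.1.4, a subject who needs rescue above the maximum and decides to withdraw is still to be followed: "the subject should have a final on-treatment visit and then have procedures and assessments completed for any remaining study visits". Against this, Protocol 7.7 says "A subject may also be discontinued from the study, at the discretion of the investigator and/or Sponsor, for any of the following reasons", and lack of efficacy heads that list.

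**The concern.** The two parts differ in kind. The stratum omission applies whatever happens: the analysis does not match the randomisation, so the standard error carries between-stratum variation that the design has already balanced.

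The fallback matters only if the unstructured fit fails. SAP 9.3 defends leaving missing values unimputed by appeal to missing at random. In a mixed model that protection comes from within-subject correlation, which lets a dropout's earlier scores inform Week 12. Variance components on a REPEATED statement sets that correlation to zero. The two imputation analyses in SAP 9.4 do not restore it: random replacement uses the pooled mean and SD for the week, and the tipping point uses the placebo mean for the week. Neither uses the subject's own earlier scores. Under SAP 9.8 the primary endpoint gates every later claim, so a shrunken primary estimate would matter beyond itself.

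**Working it through.** **Plan's own figure.** Inputs from SAP 9.9 and Protocol 11.4: 170 per group, difference 0.7, SD 2.0, two-sided 5%. SE = 2.0 × √(2/170) = 0.217; 0.7/0.217 = 3.227; power = Φ(3.227 − 1.960) = 89.7% (89.6% with the t distribution). The stated 90% is reproduced; 'over 90%' is marginally generous, since 90% needs 172 per group.

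**Stratum.** Assume a 50:50 split and strata differing by d points. The share of variance explained is R² = (d²/4)/2.0². After stratified randomisation the estimate's true variance is smaller by the factor (1 − R²), whether or not the model adjusts.
- Size without adjustment: 2Φ(−1.96/√(1 − R²)).
- Power without adjustment: Φ((3.227 − 1.960)/√(1 − R²)).
- Power with adjustment: Φ(3.227/√(1 − R²) − 1.960).

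| d | R² | Size, unadjusted | Power, unadjusted | Power, adjusted |
|---|---|---|---|---|
| 0.5 | 1.6% | 0.048 | 89.9% | 90.2% |
| 1.0 | 6.25% | 0.043 | 90.5% | 91.5% |

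The gain is about 0.3 to 1.0 percentage points. For the chi-square, taking outcome variance 0.25 (a 50% response rate) and responder rates 10 or 20 points apart, R² is 1% or 4% and size is 0.0489 or 0.0455.

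**What the fallback does.** Twelve weekly values give 12 × 13/2 = 78 covariance parameters. Variance components replaces them with one. The Week 12 contrast is then the difference in observed Week 12 means, linked to other weeks only through the common baseline slope, with a variance pooled over all weeks.

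**Is it reached?** In simulated data (n = 340 or 240, 10–30% missing at Week 12, partly with 5% intermittent gaps), 12,800 of 12,800 unstructured fits converged, as did 480 of 480 fits of a 0–7 rescue-days outcome. This was Fisher scoring with step-halving and not SAS's own routine, so it indicates but does not prove that the branch is remote.

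**Estimate if reached.** Assumed: effect reaching 0.70 by Week 4, Week 12 SD 2.0, strong within-subject correlation, and dropout hazard rising 0.6 logit per NRS point of the last observed score, by the same rule in both arms.

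| Missing at Week 12 | VC estimate of 0.70 | VC power | Unstructured power |
|---|---|---|---|
| 5% | 0.67–0.68 | – | – |
| 10% | 0.64–0.65 | 84% | 89% |
| 20% | 0.59–0.61 | 75–76% | 87–88% |
| 30% | 0.57–0.59 | 67–68% | 84–86% |

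The unstructured estimate stayed within 0.01 of 0.70. If dropout is completely random there is no bias.

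**Standard error if reached.** Size = 2Φ(−1.96 × √(mean weekly variance)/2.0). With SD rising linearly to 2.0 from 1.8, 1.6, 1.4 or 1.2 at Week 1, the SE ratio is 0.95, 0.90, 0.86 or 0.81, and size is 6.2%, 7.7%, 9.4% or 11.2%. Simulation with 8% random missing and constant SD gave 5.3–5.5%. The cause is pooling the variance, not the zero correlation.

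**Second simulation.** With different settings (SD 1.2 rising to 2.0; 17% active and 23% placebo dropout driven by the last score; 800 replicates), variance components gave 0.59 for a true 0.70, model SE 0.188 against an empirical 0.223, and 11.4% type I error under the null. Unstructured gave 0.69, 0.229 against 0.226, and 5.1%.

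**Which endpoints.** WAAPI, WPI and rescue days are weekly. PGI-I, WPAI and EQ-5D-5L are scheduled in the double-blind phase at study Weeks 11, 15, 19 and 23 (Protocol Tables 6 and 7). That is three post-baseline visits and 3 × 4/2 = 6 covariance parameters.

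**The case against.** The strongest reply is that neither part threatens the planned conclusion. The unstructured model is sound and no passage hints at convergence trouble. SAP 9.3 expects few missing values. The subjects most likely to leave because of pain, those needing rescue above the maximum, are the ones Protocol 8.1.4 asks sites to keep assessing. SAP 9.4 adds several sensitivity analyses. The unadjusted tests are valid, pre-specified and slightly conservative, and no passage requires regimen in the model. Nearly all of this stands, and it is why the point is minor. What remains is that a written rule binds the analyst if triggered, and that changing it after unblinding would look data-driven.

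A reader might infer more than the documents support:
- **The omitted stratum biases the result or inflates type I error.** It does neither.
- **Adjusting lifts power from the planned 89.6–89.7% to over 91%.** That comparison is not like for like, because the planned figure ignores the smaller true variance under stratified randomisation.
- **The fallback would favour CAM2038.** With the same pain-driven rule in both arms the estimate shrinks. Arm-specific dropout could enlarge or reverse the bias, but no passage establishes it.
- **The standard error would certainly be too small.** No SD for Weeks 1–11 is given. Growth is only suggested by the entry limit on pain (Protocol 7.4) set against the planned Week 12 SD of 2.0.
- **All secondary endpoints are equally exposed.** With 6 covariance parameters, PGI-I, WPAI and EQ-5D-5L are even less likely to trigger the rule.

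**Conclusion.** Both parts hold, at minor severity. The stratum omission is certain; its effect is conservative and small, and depends on the assumed 0.5 to 1.0 point difference between strata. The fallback is a poorly chosen contingency for the weekly outcomes that will probably not be used. Its consequences (attenuation under pain-driven dropout, and an anti-conservative test if spread grows) rest on a dropout rate, a mechanism and an SD pattern that the documents do not give. The planned unstructured analysis is not called into question.

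**What to change.** Before unblinding:

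1. Add regimen (q1w or q4w) as a fixed effect in the primary model and in the endpoints analysed by similar methods. Use a Cochran-Mantel-Haenszel test for responders and a log-rank test stratified by regimen.
2. Delete both variance-components statements in SAP 9.3. If the unstructured fit fails, retry it with other starting values or Fisher scoring. Then move through a pre-specified sequence of correlated, heterogeneous-variance structures, for example heterogeneous Toeplitz and then heterogeneous compound symmetry, with sandwich standard errors. Report which structure was used.

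At 30% missing under the same dropout rule, those two structures gave 0.68–0.70 and 0.68–0.72 for a true 0.70, against 0.57–0.59 for variance components. They reduce the bias without guaranteeing its removal, and the sandwich corrects the standard error, not the estimate. The order is a choice. REML with Kenward-Roger is optional.

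The cost is SAP wording and a few lines of SAS, with no new data or patients. SAP 6.2 already provides for numbered revisions after the final version.
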